#### 12.2 Analysis Populations

## **Evaluable participants for efficacy**

• All participants who receive at least 1 dose of study drug(s) will be evaluated for the primary endpoint. Participants who develop rapid symptomatic disease progression

- or drop out early due to death will be treated as non-responders. Participants who develop early toxicities that require treatment delay or discontinuation will continue to be evaluable on study.
- Participants may be replaced in either arm if they complete randomization but do not complete any cycles of therapy.

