**Table 3: Schedule of Assessments** 

	Baseline/ Screening a	Cycle 1 b	Cycle 2	Cycle 3	Cycle 4	Follow-up Visit 1 and 2 d	Additional Follow-up Visits e	Early Termination Visit f
Obtain Informed Consent	X							
Participant History	X							
Inclusion/Exclusion criteria	X							
Biopsy of Target Lesion c	X	X						
Prior/concomitant medications	Collected from Screening to Follow-up							
Physical Examination	X	X	X	X	X	X		X
Performance status	X	X	X	X	X	X		X
Height/Weight	X	X	X	X	X	X		X
Vital Signs	X	X	X	X	X	X		X
Complete Blood Count	X	X	X	X	X	X		X
Complete Metabolic Panel, LDH	X	X	X	X	X	X		X
Thyroid function testing g	X	X	X	X	X	X		X
Pregnancy test (serum)	X	X	X	X	X	X		X
HCV, HBV, HIV Testing	X							
CT scan h	X				X	X		X
MRI Brain	X							
ECG	X							
Adverse Events	Collected from consent to 100 days after drug discontinuation							
Drug Administration		X	X	X	X			
Research blood (~40mL)	X	X	X	X	X	X		X

PD-L1 expression on banked tumor specimen if available	X					
Survival Data				X	X	X

<sup>aScreening assessments are recommended to be performed within 28 days prior to treatment unless otherwise specified above

<sup>bEach cycle=21 days±4 days

<sup>cBiopsy at baseline for all participants within 14 days of Cycle 1, Day 1. On-treatment biopsy must be performed within 14 days±5 days of first dose of study drug.

<sup>dFollow up period begins when the last dose of study therapy is administered. Follow-up visit 1=21 days from last dose  $\pm$  7 days. Follow-up visit 2=42 days from last dose  $\pm$  7 days. If the participant completed follow-up visit 1 and follow-up visit 2 and *has* progressed, the participant is not required to have scans every 12 weeks. Survival could be assessed via calls every 3 months ( $\pm$ 7 days). If a participant is off treatment and *has not* progressed, they would continue to visit the site and have scans every 12 weeks.

 $^{\rm e}$ Additional follow-up visits will be scheduled every 3 months  $\pm 7$  days. For participants who end treatment for toxicity, scans should continue every 12 weeks until progression of disease. After progression of disease, survival calls will occur every 3 months ( $\pm 7$  days).

<sup>fFor participants who terminate the study early, follow-up will begin 21 days from the last dose (follow-up visit 1).

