#### 12.1 Determination of Sample size

Twelve participants will be enrolled in each arm for a total of 24 participants. A response rate of 10% or less would not be considered promising (null hypothesis) as the ipilimumab response rate in untreated patients is 10.9%. A response rate of at least 30% is promising (alternative hypothesis). Point estimates and 95% confidence intervals for the response rates will be reported. Alpha (probability of Type I error) for hypothesis tests will be 0.1. If 4 or more of 12 participants in an arm respond (response rate of 33% or greater), the treatment will be considered promising for further investigation.

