3 STUDY DESIGN

Study PIC10001 is a multi-center, randomized, Phase 2 study of ipilimumab vs ipilimumab plus nivolumab in participants with unresectable Stage III or Stage IV melanoma who were refractory to PD-1 inhibitor monotherapy.

There will be two treatment arms in this study:

Arm A: Participants will receive combination checkpoint blockade with ipilimumab and nivolumab.

[figure not shown]
Arm B: Participants will receive ipilimumab alone.

Participants who are eligible will be required to have a pre-treatment biopsy and then will be randomized to either ipilimumab alone or ipilimumab in combination with nivolumab. Participants will receive treatment for up to 4 cycles followed by an observation phase.

The primary objective is to determine the response rate of combination ipilimumab/nivolumab and ipilimumab alone in participants previously treated with a PD-1 inhibitor by Week 18 of therapy. The total planned enrollment is 24 total participants, with 12 participants randomly allocated to each arm. Participants will be assessed for the primary endpoint at Week 18. They will then be followed for time to treatment failure (TTF) and overall survival (OS) for up to 2 years.

The study design is depicted in Figure 1.

Figure 1: Study Schema

Note: The on-treatment biopsy has a window of ± 5 days.

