3.4 Determination of Sample Size

This study is not intended or powered for hypothesis testing. The study is intended to provide preliminary estimates of adverse events, response rates, effect sizes and confidence intervals. A sample size of approximately twelve participants in each arm, for a total of 24 participants, will provide these preliminary estimates. The study protocol incorrectly states that a Simon 2-stage design will be implemented for this study. A 2-stage design was not implemented; rather, a single-stage design was used.

Table 1 provides 95% exact confidence intervals for the proportion of responders per treatment arm. These confidence intervals provide information needed for the design of future studies.

Table 1: Confidence Intervals for the True Proportion of Responders

Observed responder rate	95% Confidence Interval (n = 12)
8.3% (1/12)	(0.2%, 38.5%)
16.7% (2/12)	(2.1%, 48.4%)
25.0% (3/12)	(5.5%, 57.2%)
33.3% (4/12)	(9.9%, 65.1%)

41.7% (5/12)	(15.2%, 72.3%)
50.0% (6/12)	(21.1%, 78.9%)

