5.1.2 Safety-Evaluable Population

The safety-evaluable population, also referred to as the toxicity-evaluable population in the study protocol, will include all participants who received at least one dose of any study intervention (ipilimumab or nivolumab). Note that this is a more conservative definition than

the toxicity-evaluable population defined in the Protocol, which includes all participants who completed at least one cycle on either treatment arm. For analyses based on this population, participant treatment groups will be defined according to the treatment that was assigned at randomization. However, if a participant received the incorrect study drug for the entire period of treatment, the participant's treatment group will be defined as the incorrect drug the participant actually received.

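### Evaluability starts at one dose but replacement at an incomplete cycle, so a dosed early failure may be both counted and replaced, and the 4-of-12 rule does not say what happens above 12

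*Protocol*

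**What the plan says.** Protocol 12.2 sets the evaluability trigger at one dose: "All participants who receive at least 1 dose of study drug(s) will be evaluated for the primary endpoint". Rapid symptomatic progressors and early deaths count as non-responders. The next bullet sets the replacement trigger: "Participants may be replaced in either arm if they complete randomization but do not complete any cycles of therapy". The same pair of rules stands in the Protocol synopsis and in the synopsis appended to the SAP (8.1). Protocol 7.3 has replacement in its title but gives no rule.

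The documents give cycle more than one meaning:
- Protocol Section 8, under Arm A and Arm B, equates one cycle with one dose (in Arm A, both drugs given together).
- Protocol Table 3, footnote b: "Each cycle=21 days±4 days".
- SAP 5.1.2 contrasts its own population, defined by one dose of either drug, with "the toxicity-evaluable population defined in the Protocol, which includes all participants who completed at least one cycle on either treatment arm". It treats the two as different sets.

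The sample size is 12 per arm. Protocol 12.1 says "Twelve participants will be enrolled in each arm for a total of 24 participants", SAP Section 3 says "with 12 participants randomly allocated to each arm", and SAP 3.4 is looser: "A sample size of approximately twelve participants in each arm". The decision rule in Protocol 12.1 begins "If 4 or more of 12 participants in an arm respond" and glosses this as a rate of at least 33%.

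**The concern.** The two triggers sit in adjacent bullets and do not match. If a cycle is a 21-day period, a participant who is dosed on Day 1 and dies or progresses on Day 10 is evaluable, is a non-responder, and has not completed a cycle. That participant may therefore be replaced.

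The replacement bullet is permissive. It names no decision-maker and no criterion, and the trial is not blinded. Whether an arm stops at 12 or goes on could then depend on early outcomes that the people deciding can see. The 4-of-12 rule and the SAP's table of confidence intervals are both written for exactly 12.

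**Working it through.** **Inputs.** From Protocol 12.1: n = 12 per arm, null rate 10%, alternative 30%, alpha 0.1, cutoff four responders or 33%. The documents give no rate of failure during the first cycle.

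**Step 1: reproduce the plan's rule.** With X ~ Binomial(n, p), the false-positive chance is P(X ≥ r | p = 0.10) and power is P(X ≥ r | p = 0.30).
- n = 12, r = 4: error 0.0256, power 0.507.
- n = 12, r = 3: error 0.1109, power 0.747.

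Four is therefore the smallest cutoff with error at or below 0.1, and 4/12 = 33.3% agrees with the 33% gloss. The cutoff reproduces, with 0.1 as a ceiling rather than the attained level. The six exact intervals in SAP Table 1 also reproduce (4/12: 9.9% to 65.1%).

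**Step 2: who can be both evaluable and replaceable?**

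| Meaning of a completed cycle | Dosed in full, fails on Day 10 | Arm A, nivolumab only or stopped infusion |
|---|---|---|
| One dose given (Protocol Section 8) | Evaluable, not replaceable | Evaluable, arguably replaceable |
| 21 ± 4 days (Protocol Table 3) | Evaluable and replaceable | Evaluable and replaceable |

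The right-hand column arises because nivolumab is infused first (Protocol 8.4.1), an Arm A cycle needs both drugs, and SAP 5.1.1 requires only a dose of either. The nivolumab-only route exists in the combination arm alone.

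**Step 3: what happens to the denominator?** SAP 5.1.1 and 5.4 include every randomized and dosed participant. SAP 5.4.1 counts those without a post-baseline scan as non-responders. A replaced dosed participant therefore stays in, and with k such replacements n = 12 + k.

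**Step 4: apply the rule to n above 12.** A 33% rate requires 0.33 × 13 = 4.29, 0.33 × 14 = 4.62 or 0.33 × 15 = 4.95 responders, so five in each case.

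| n | 4/n | Cutoff 4: error / power | Cutoff 5: error / power |
|---|---|---|---|
| 12 | 33.3% | 2.6% / 50.7% | not needed |
| 13 | 30.8% | 3.4% / 57.9% | 0.6% / 34.6% |
| 14 | 28.6% | 4.4% / 64.5% | 0.9% / 41.6% |
| 15 | 26.7% | 5.6% / 70.3% | 1.3% / 48.5% |

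The two halves of the rule diverge from n = 13 onward. The exact interval for four responders moves from 9.9%–65.1% at n = 12 to 9.1%–61.4% at n = 13 and 8.4%–58.1% at n = 14.

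**Step 5: a check on the approximation.** The table treats n as fixed, whereas an extra place would open only after an early failure. Assume that a share q of dosed participants fails in the first cycle, that none of them responds, and that all are replaced. The responder count then follows Binomial(12, p/(1 − q)). At p = 10%, P(X ≥ 4) is 3.0%, 3.6% and 5.3% for q = 5%, 10% and 20%. These q values are assumptions. The error is of the same order as in the table.

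**The case against.** The strongest reply is that Protocol Section 8 itself equates one dose with one cycle, so the 21 days can be read as the dosing interval. SAP 5.2 also speaks of receiving a cycle. On that reading a participant fully dosed on Day 1 who fails on Day 10 is not replaceable, and only a rare partial dose remains. SAP 5.1.2 separates a dose from a completed cycle but does not define a cycle, and partial dosing alone could explain the distinction. This stands as far as it goes: it makes the wider overlap possible rather than certain. It does not settle which meaning governs the replacement bullet.

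A reader might also infer that replaced early failures leave the analysis and so inflate the response rate. The documents do not support this. Protocol 12.2 and SAP 5.1.1, 5.4 and 5.4.1 all keep dosed participants in the denominator, and both documents say that the SAP prevails where they differ.

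Finally, the SAP disclaims hypothesis testing, plans only approximately 12 per arm, does not use the 4-of-12 rule in its body, and computes Clopper-Pearson intervals on the actual number. All of that is right, and it limits the consequence. But the SAP settles who is analysed, not who is enrolled. Its body has no replacement rule, its Section 6 lists no change to replacement or to the cutoff, and its appended synopsis repeats both.

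**Conclusion.** The point holds as an inconsistency of modest size. The evaluability and replacement triggers differ, cycle has no single meaning, and an arm can exceed 12 through a choice that may follow early outcomes. Once it does, the count and the rate in the decision rule give different answers for an arm with exactly four responders, and neither document says which governs.

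With one or two extra participants, keeping four raises the error from 2.6% to 3.4% or 4.4%. Keeping 33% lowers power from 51% to 35% or 42%. Error stays below the stated 0.1 in every case shown. The figures assume independent binomial responses and one or two replaced participants who remain in the denominator. How often replacement would occur cannot be derived from the documents.

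**What to change.** In the Protocol synopsis, Protocol 12.2 and the synopsis in SAP 8.1, replace the bullet with: *Only randomized participants who receive no study drug may be replaced. Every dosed participant stays in the denominator and is not replaced.* Reconcile the meaning of a cycle between Protocol Section 8 (Arms A and B) and Table 3. Add the number replaced, by arm, to the disposition summary in SAP 5.2, which does not show it explicitly. With that change replacement no longer takes the dosed number above 12, and the rule keeps its error of 2.6% and power of 51%.

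If a dosed participant has already been replaced, keep both that participant and the replacement in the analysis and state the cutoff for the actual n. Four remains the smallest cutoff with error within 0.1 at n = 13 to 15, since a cutoff of three already exceeds 0.1 at n = 12. If four is kept, the 33% gloss should be dropped.

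The cost is a sentence in three places, a definition and one reporting line. The sponsor gives up the option of adding a participant after an early failure.

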# Evaluable participants for toxicity

Participants who have completed at least one treatment cycle on either arm will be considered evaluable for toxicity.

## 12.3 Efficacy Analysis

## 12.3.1 Analysis of Primary Efficacy Endpoint

• The primary endpoint is objective response (CR and PR) as defined by RECIST criteria by Week 18. Objective response rates will be estimated as proportions with 95% CIs estimated using an exact procedure.

## 12.3.2 Analysis of Secondary Efficacy Endpoints

- DCR, defined as participants who achieve SD, PR or complete response at Week 12 and/or Week 18 as measured by RECIST v1.1 will be estimated as proportions with 95% CIs estimated using an exact procedure.
- Participants will be followed for duration of response (in those participants who derive clinical benefit), TTF and OS for two years; these will be estimated and demonstrated using Kaplan Meier approaches.

## 12.3.3 Analysis of Exploratory Efficacy Endpoints

- All research samples for exploratory endpoints will be analyzed at a Parker Institute for Cancer Immunotherapy selected testing center. Please see Appendix 3 for further information.
- Peripheral lymphocyte phenotype changes throughout treatment, including Treg cells, defined as CD4+FOX3P+ cells, will be expressed using descriptive statistics at pre and post treatment time points. These will be assed via flow cytometry of PBMCs.
- Changes in quantities of MDSCs, defined as CD14+HLA-DRlow cells, throughout treatment will be expressed using descriptive statistics at pre and post treatment time points.
- nCounter immune profiling of the tumor before treatment will be expressed using descriptive statistics at pre and post treatment time points and will be correlated with clinical response also using logistic regression models.
- Tumor neoepitopes and mutational burden will be correlated with clinical response also using logistic regression models.
- Summary statistics will be generated and differences between mutation burden or neoantigen score as they relate to PD-L1 expression

- IHC will be used to assess PD-L1 expression on both immune cells and tumor cells. PDL-1 expression will be assessed pre-treatment and on-treatment. A participant will be PD-L1 + if > 1% of cells express PD-L1. If response data permit, the tumor positivity of PD-L1 expression will be compared in the pre- and post-treatment biopsies using a Wilcoxon signed rank test.
- Pre- and on- treatment PD-L1 expression and will be correlated with clinical response also using logistic regression models.
- IHC will be used to quantify cytotoxic and Tregs, including stains for CD3, CD4, CD8, FOXP3, ICOS and Lag3. Associations from pre to post treatment will be assessed using the Wilcoxon signed rank test for paired comparisons (e.g., the continuous measure, density of cells per high powered field).

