5.4.3 Exploratory Efficacy Endpoints

Exploratory endpoints defined in the protocol are outside the scope of this SAP.

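### The biomarker–response logistic regressions have no small-sample method for about 3 to 7 responders, so binary PD-L1 models may have no finite odds ratio and continuous-marker estimates will be very variable

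*Protocol*

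**What the plan says.** Protocol 12.3.3 (Analysis of Exploratory Efficacy Endpoints) states that "Tumor neoepitopes and mutational burden will be correlated with clinical response also using logistic regression models" and that "Pre- and on- treatment PD-L1 expression and will be correlated with clinical response also using logistic regression models". The nCounter immune profile is handled in the same way. The section calls a participant PD-L1 positive when more than 1% of cells express the protein, but it does not say whether the models use that binary coding. Estimator, covariates, pooling of arms and a fallback for sparse data are all unstated. The one proviso about adequate response data is attached to the pre/post PD-L1 signed-rank comparison, not to the logistic models.

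On size, Protocol 12.1 says "Twelve participants will be enrolled in each arm for a total of 24 participants". The same section takes 10% as the unpromising response rate, citing 10.9% for ipilimumab, and 30% as the promising one.

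The SAP adds no detail. Section 5.4.3 says "Exploratory endpoints defined in the protocol are outside the scope of this SAP". The covariate adjustment in SAP 5.4 covers primary and secondary endpoints only, and SAP 6 lists no departure for the biomarker models. The synopsis reproduced in SAP 8.1 repeats them unchanged.

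The Protocol's Document History records the cut from 70 to 24 participants in the March 2018 version and ties it to Sections 6.1, 6.2 and 12.1. Section 12.3.3 is not among them.

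**The concern.** Logistic regression depends on the size of the smaller outcome group, which here is the responders. With only a handful, two things go wrong under maximum likelihood. If a binary marker leaves any cell of the marker-by-response table empty, or a continuous marker splits responders from non-responders completely, the odds ratio has no finite estimate. When the estimate is finite, its sampling distribution has a long tail.

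Relating tumour neoepitopes and mutational burden to response, and response to PD-L1, are stated exploratory objectives (Protocol 5.1.3) that rely on required biopsies. SAP 3.4 describes the study's purpose as preliminary estimation, including effect sizes and intervals. The plan already uses exact intervals for response rates. The biomarker models are where small-sample handling is missing.

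**Working it through.** **Inputs.** From the documents: N = 24 (12 per arm); response rates 10.9% and 30%; PD-L1 positivity as a yes/no class. Assumed, because the documents give no figure: PD-L1 prevalence q of 30% or 50%; a standard normal continuous marker with a true odds ratio of 2 or 3 per SD; 20% as a middle response rate; response meaning CR or PR by Week 18; no missing samples.

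**The plan's own figure.** The documents give no power or event count for these models. The nearest stated figure is SAP Table 1. For 4/12 the Clopper-Pearson limits are the 2.5% point of Beta(4, 9) = 9.9% and the 97.5% point of Beta(5, 8) = 65.1%, as printed. The other five rows also reproduce.

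**Expected responders (N × p).** 24 × 0.109 = 2.6; 24 × 0.20 = 4.8; 24 × 0.30 = 7.2. Per arm: 1.3 to 3.6. At the former size: 70 × 0.109 = 7.6 to 70 × 0.30 = 21.

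**Binary PD-L1, no true effect.** The four cells have probabilities pq, p(1−q), (1−p)q and (1−p)(1−q). The chance that at least one is empty follows by inclusion–exclusion. For p = 0.109, q = 0.5, N = 24:

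- each responder cell is empty with probability (1 − 0.0545)^24 = 0.2605
- there are no responders at all with probability (1 − 0.109)^24 = 0.0627
- the remaining terms are negligible, so P = 2 × 0.2605 − 0.0627 = 0.458

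The same formula elsewhere (50% positive, then 30% positive):

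| Response rate | N = 24, pooled | N = 12, one arm | N = 70 |
|---|---|---|---|
| 10.9% | 45.8%, 53.7% | 77.1%, 81.4% | 3.9%, 10.1% |
| 20% | 15.5%, 25.0% | 50.0%, 59.2% | 0.1%, 1.3% |
| 30% | 4.0%, 11.1% | 28.1%, 41.2% | 0.0%, 0.1% |

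Adding arm cannot lower these figures, because data separated by the marker alone remain separated in the larger model.

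**One continuous marker, N = 24, true odds ratio 2 (log 0.69), simulated.**

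| Response rate | No finite estimate | Mean ML log OR | Excess over 0.69 |
|---|---|---|---|
| 10.9% | about 10% | 0.98–0.99 | 41–43% |
| 20% | about 1% | 0.91–0.92 | 31–33% |
| 30% | under 1% | 0.87 | about 25% |

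The mean and excess are among estimable trials. The median odds ratio is about 2.1 to 2.2, so the excess in the mean comes from a tail of nearly separated data sets. At a true odds ratio of 3 the failure rates are 13%, 2% and 0.3%.

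With arm added (true odds ratio 2), some coefficient is non-finite in 46%, 14% and 3% of trials. The marker's own coefficient is infinite in 13%, 2% and 0.3%, so arm is usually the term that fails. Fitted within one arm, 38%, 15% and 6% of trials give no finite estimate.

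**Direction of bias, binary marker.** With no true effect and 50% positive, estimable log odds ratios centre on zero (means −0.002 to −0.010). At a true odds ratio of 3 and 50% positive, the geometric mean of finite estimates is 1.5, 2.5 and 3.0 with 3, 5 and 7 responders. At 30% positive it is 3.0, 3.1 and 3.4.

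**Firth, same continuous marker.** With 3, 5 and 7 responders the mean log odds ratio is 0.71, 0.70 and 0.69 against 0.69; maximum likelihood gives 0.98, 0.88 and 0.88. At a true odds ratio of 3 (log 1.10), Firth gives 1.08, 1.12 and 1.23 against 1.53, 1.43 and 1.40. At a 20% response rate and a true odds ratio of 2, root mean squared error is 0.70 for Firth and 1.16 for maximum likelihood.

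**The case against.** The analyses are exploratory, no decision rule depends on them, the SAP disclaims hypothesis testing, and an analyst would notice a non-finite estimate. All of that stands and limits the importance of the point.

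Several stronger readings are tempting, and the documents do not support them:

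- **That the neoepitope and mutational-burden odds ratios will often be undefined.** These markers are naturally continuous. For one such marker in the pooled sample, failure is uncommon: 0–3% given 3, 5 or 7 responders, and about 10% only when the rate is 10.9% and the responder count is left to chance. The high failure rates belong to binary PD-L1, to models with arm or stratum added, and to fits within an arm.
- **That every finite estimate exaggerates the association.** This holds on average for a continuous marker. For a binary marker the bias can be absent, toward 1 or slightly away from it.
- **That the plan commits to the wrong estimator.** It says only logistic regression, and Firth's method is a form of that. Maximum likelihood is the usual reading, not a stated choice.
- **That the intervals will produce false signals.** No interval method is named. In simulation, nominal 95% Wald intervals for the continuous marker covered 97.8–98.6% (odds ratio 2) and 97.0–99.6% (odds ratio 1) among estimable fits, which is conservative.

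Nor does Firth rescue every failure. At 10.9%, 6.3 of the 45.8 percentage points are trials with no responder, where no model can be fitted.

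**Conclusion.** The point holds in a limited form. The protocol plans biomarker–response regressions with no small-sample provision, for a trial expected to yield about 3 to 7 responders, and the SAP leaves that in place. If PD-L1 enters as a binary marker, the chance of no finite odds ratio runs from about half at a 10.9% response rate to 4–11% at 30%. At 70 participants it would have been about 10% or less throughout, so most of the problem comes from the reduced size. For a continuous marker the main problem is variability, with inflation in the mean but little in the median.

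These figures rest on the assumed prevalence, a normal marker, the true odds ratios used, complete samples and maximum likelihood. Missing tissue would make matters worse: with 18 participants, an assumed figure, a continuous marker fails in 17%, 5% and 1% of trials at the three response rates. The primary and secondary results are unaffected. This is a worthwhile, optional improvement.

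**What to change.** State that each biomarker–response model is fitted by Firth penalised likelihood with profile-likelihood intervals, one marker per model. Pool the arms for pre-treatment markers. For on-treatment PD-L1, include arm as a term: that marker is measured after randomised treatment begins, so arm may affect both it and response, and unadjusted pooling could confound the association. Say how PD-L1 is coded, give the number of responders beside each estimate, and report the results descriptively.

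The cost is about one sentence and a standard option in SAS and R. Changing Protocol 12.3.3 needs a formal amendment submitted to the IRB/IEC (Protocol 13.8.1). Since the SAP supersedes the protocol where they differ, the sentence could instead replace the exclusion in SAP 5.4.3, before database lock. The statistical downside is slight shrinkage toward no effect. Firth also needs at least one responder, one non-responder and a marker that varies, and intervals will remain wide.
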